Prior treatments for onchocerciasis using diethylcarbamazine and ivermectin

The use of DEC and its associated adverse events in individuals with heavy infections with onchocerciasis was recently reviewed by the study team²⁶. The discussion below summarizes some key points from that publication. Prior to 1987, an 8 to 14 day course of diethylcarbamazine (DEC) was commonly used to treat onchocerciasis. DEC was an effective microfilaricide, but it occasionally was associated with the development of severe inflammatory responses—both systemic and dermal—caused by the death of Mf. This is referred to as a Mazzotti reaction. DEC also caused adverse events in the eye, with punctate and sclerosing keratitis, limbitis, anterior uveitis, and chorioretinitis. It sometimes caused optic neuritis with edema and visual impairment in individuals with heavy *O. volvulus* infection who received high doses of the drug for prolonged periods^{9, 28}.

During the 1980's a single dose of IVM was shown to be more effective than DEC for clearing the Mf from the skin with minimal ocular adverse effects²⁹, and it has been the treatment of choice since that time. IVM reduces *O. volvulus* Mf numbers in skin within a few days with a nadir of skin Mf between 1 and 3 months post-treatment. Mf may reappear in the skin as early as 3 months post-treatment³⁰. Mf clearance from the eye following IVM treatment is slower by several months than clearance observed in the skin^{6, 31}. The nadir of Mf clearance from the anterior chamber of the eye starts 6 months post-treatment based on unpublished results from heavily infected subjects in the Volta region of Ghana with ocular Mf (Table 1), and that reduction persisted out to 18 months after treatment³².

Table 1. Kinetics of Mf clearance from the anterior chamber of the eye following IVM treatment

Visit (Days/months post IVM 150 mcg/kg treatment)	Subjects with ≥ 1 Mf in the anterior chamber of both eyes before and following a single dose of IVM n/N (%)
Day 0 (pretreatment)	205/205 (100)
Day 3	145/174 (83.3)
Day 4	21/23 (91.3)
Month 1	90/201 (44.8)
Month 6	14/200 (7.0)
Month 12	16/195 (8.2)
Month 18	13/160 (8.1)

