The clearance of Mf from the posterior chamber of the eye is poorly understood because it is more difficult to visualize this part of the eye. Several studies have shown that anterior segment lesions such as punctate keratitis, sclerosing keratitis, iridocyclitis improved after IVM^{33, 34}, but there are conflicting data about the effectiveness of IVM for improving vision or preventing visual loss related to posterior segment lesions.

The [name] et al. review also discussed the possibility for re-introducing DEC in combination with ivermectin and albendazole, referred to as IDA for treatment of onchocerciasis²⁶. The reason for this is that IDA has been found to be much more efficacious for treatment of lymphatic filariasis (LF)³⁵. This study along with a large multicenter safety study (manuscript development in progress) resulted in the World Health Organization changing its guidelines to recommend IDA for LF outside Africa³⁶. Based on this recommendation Merck Sharp & Dohme Inc agreed to increase

their donation of ivermectin by 100 million doses per year for use of IDA in MDA programs for LF outside of sub-Saharan Africa³⁷. LF is often co-endemic with onchocerciasis in sub-Saharan Africa. This raises the important question of whether IDA can be safely used for LF elimination in coendemic areas. We hypothesize that IDA will be safe for use in persons with onchocerciasis if dermal and ocular Mf are cleared or greatly reduced by pretreatment with ivermectin alone

Many studies have examined Mf clearance from the skin after IVM treatment and these have been summarized in a meta-analysis³⁸. These results show microfilaridermia are reduced by half after 24 h, by 85% after 72 h, by 94% after 1 week, and by 98-99% after 1-2 months. Mf reappear in the skin as early as 3 months post-treatment³⁸.

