Secondary Objectives:	
Safety:
 
 1. To compare rates of adverse events grade 3 or higher by treatment group that occur within 7 days of treatment in the subset of participants who have intraocular microfilariae just prior to treatment with IDA to those who do not have intraocular microfilariae 2. To compare rates of ocular adverse events (any grade) by treatment group that occur within 3 months of treatment with IDA 
Efficacy
 
 1. To compare the effect of three treatment regimens for killing adult female O. volvulus worms based on the percentage of all adult female worms in nodules that are alive 18 months after treatment. 2. To compare the effects of three treatment regimens for complete clearance of microfilariae from skin snips 3, 12 and 18 months after treatment with IDA. 3. To compare the effects of three treatment regimens for preventing reappearance of microfilariae in the skin at 12, and 18 months after treatment with IDA.

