4.2 Inclusion and Exclusion Criteria

Inclusion Criteria

1. Men and women 16 – 70 years (at the time of enrollment; ± 2 years) of age previously enrolled in the Part 1 study and residing in the area of the study.
2. Participants must have at least 1 palpable subcutaneous nodule (onchocercoma).
3. Participants with baseline skin Mf counts ≥ 3 Mf/mg at the time of enrollment into the Part 1 study (Part I, see above).

Exclusion Criteria

1. Pregnant and breastfeeding mothers within 1 month of giving birth
2. Severe eye disease at baseline including uveitis, severe glaucoma, , severe keratitis, and/or cataracts that interfere with visualization of the posterior segment of the eye as well as the list of ocular diseases as outlined below Individuals who are excluded with significant ocular disease will be referred to appropriate ophthalmological care in a health facility (the district hospital) or the any other health facility in Ghana, where affected subjects will obtain appropriate care (University hospital or private ophthalmologist). All ocular disease exclusion criteria apply to either eye. Bilateral disease is not necessary to exclude a participant. A participant will be excluded if any of the criteria are met for one eye.
 - a. Any cataract of any type preventing clear visualization of fundus or imaging on Optical Coherence Tomography (OCT).
 - b. Severe retinal nerve fiber layer thinning in the superior and inferior quadrant analysis on Ocular Coherence Tomography of the optic nerve with a corresponding visual field defect of grade 2 or worse on the same eye.
 - i. If Ocular Coherence Tomography is not available, the following exclusion criteria will apply: vertical Cup/disc ratio on fundoscopy (not by OCT reading) greater than or equal to 0.80.
 - c. Intraocular pressure (IOP) greater than or equal to 25 by Goldmann tonometry.¹²
 - d. Retinal Detachment or Retinal Break
 - e. Acute ocular infection (i.e., Viral conjunctivitis, corneal ulcer, endophthalmitis)
 - f. Optic Atrophy with visual field defect reproducible on confrontation visual field testing..
 - g. Exam consistent with Herpes Simplex Virus eye infection
 - h. Homonymous hemianopsia, quadrantsopsia, bitemporal hemianopsia, or central scotoma related to cerebral vascular disease by Automated Visual Field testing and confrontation visual field testing.
 - i. Acute Angle Closure Glaucoma
 - j. Gonioscopy grade 0 (slit) limiting ability to safely dilate patient

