4.7 Participant Treatment

At baseline, participants will be given ivermectin (150 $\mu\text{g}/\text{kg}$) pretreatment. This pretreatment will be provided the participants' villages near their homes following their consenting to participate in the study. *Please note, *all participants* will be treated with ivermectin at baseline to ensure that they have low skin and ocular Mf counts at the time of enrollment. (This treatment is *in addition to* the pretreatment with ivermectin given in the Part I study).

After the baseline treatment with ivermectin alone, participants will be randomly assigned to one of the following treatment arms (all oral medications)*:

I. Ivermectin 150 $\mu\text{g}/\text{kg}$ plus albendazole (400 mg)

II. IDA single oral dose

- a. Ivermectin, 150 $\mu\text{g}/\text{kg}$

- b. Diethylcarbamazine citrate, 6 mg/kg
- c. Albendazole, 400 mg

III. IDA three one time daily oral doses

- a. Ivermectin, 150 μ g/kg
- b. Diethylcarbamazine citrate, 6 mg/kg
- c. Albendazole, 400 mg

Randomized treatment to one of the three treatment arms will occur in cohorts of up to 20 individuals. This is based on the project's capacity for transport, examination, and housing of participants. Initial participants will be individuals who had zero Mf in the eyes six months after pre-treatment with IVM in Part I and zero Mf in the eyes at baseline for Part II. If IDA proves safe in all of these participants,(i.e. if there are no serious or severe adverse events in *any* participant in the first 7 days) the study will continue with participants who had Mf in the anterior chamber in either eye six months after IVM pre-treatment in the Part I study or at the baseline exams for this study. Study investigators will monitor the safety of the participants in each treatment cohort for 7 days before dosing the next cohort, and they will suspend the study if any treatment-related serious or severe adverse events occur. If SAEs are reported, the DSMB will be asked to review the cases and to implement study stopping and pausing guidelines if the SAEs are found to be related to study treatments.

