8 STATISTICAL CONSIDERATIONS

8.1 Sample Size Determination (Power calculation)

The *primary outcome* variable used for our power analysis is the % fertile female worms (100 x fertile female worms/ total female worms) for each of the three drug treatments: (1) single-dose IVM (IVM alone); (2) single dose of IVM + DEC and albendazole (IDA1); (3) three daily doses of IVM + DEC and albendazole (IDA3). Power calculations for our primary treatment-group comparison (IVM /ALB vs IDA1) assumed that 30% of the total worms will be fertile females in IVM/ALB group and that 15% of the total worms will be fertile females in the IDA1 group. For our secondary treatment-group comparison (IVM/ALB vs IDA3), we assumed that 10% of the total worms were fertile females for the IDA3 group. On average, we assumed that there will be 6 total female worms to evaluate in 3 nodules per person after treatment. In our analysis we treated each worm within a subject as a Bernoulli trial (0=non-fertile female worm, 1=fertile female worm), and we used an intra-class correlation (ICC) of 30% to account for within subject correlation among the trials. The ICC and cluster size (# female worms/person) adjusts the sample-size estimate using the following formula: $1 + \text{ICC} \times (\text{Cluster size} - 1)$ ^{44, 45}. To achieve 80% power at a two-sided alpha-level of 0.05, we will need nodule histology data from 51 subjects in each treatment group for the primary treatment-group comparison (IVM/ALB vs IDA1). The expected % difference for our secondary treatment-group comparison (IVM/ALB vs IDA3) powered at 80% and an alpha of 0.05, would require 26 subjects/group. After accounting for a 20% drop-out rate, a sample size of at least 61 subjects per treatment group will enable us to address both the primary (IVM/ALB vs IDA1) and secondary (IVM/ALB vs IDA3) treatment-group comparisons. Furthermore, we will attempt to enroll additional subjects beyond the target of 61 to provide some protection against other (unforeseen) factors that could decrease the power of this study (e.g., within village correlation, smaller effect size, higher drop-out rate than anticipated). The study will provide preliminary safety data, but a much larger study will be required to provide a precise safety comparison of IVM/ALB vs IDA.

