8.2 Data Analysis Plan

Efficacy analysis for primary outcome

Because of the within subject correlation for the primary outcome (% fertile female worms), we will use a generalized linear mixed model approach (PROC GLIMMIX, SAS)⁴⁶. Generalized linear mixed models (GLMM) permit modeling of non-normal outcomes while accounting for correlation among observations within a group. In the present study, the primary outcome is binary (0=non-fertile female worm, 1=fertile female worm) and worms within a person are not independent. To model these data we will use a GLMM assuming a binomial distribution with a logit link function,

and person will be treated as a random effect. Further, while we do not anticipate an effect of village on our outcomes, if subjects within village are correlated the GLMM can be extended to account for this correlation. A two-sided P -value ≤ 0.05 is considered significant for these analyses.

Efficacy analysis for secondary outcomes

Similar to the analysis of the primary outcome, percentage of all adult worms that are viable will be analyzed using a GLMM. Percent of persons with zero MF at 18 months will be analyzed using a generalized linear model assuming a binomial distribution and a logit link function. The difference between pre and post treatment MF counts (% reduction) will be analyzed using a paired t-test and will be transformed as necessary to meet the assumptions of this analysis. A P -value of 0.05 will be considered significant for all secondary outcomes.

Safety

The primary safety analysis will focus on AEs with severity grade 3 or greater. Secondary analyses will separately consider all AEs and ocular AEs. AEs will be assessed daily for 7 days after treatment and 3 months after treatment. This will include general assessments and detailed ophthalmological examinations on day 7 and 3 months after treatment. AE rates and severity will be compared across the three treatment groups using logistic regression analysis; with Student's t -test will be used to assess differences for individual AEs. The data will also be examined using a generalized linear mixed model that as described below can model non-normal outcomes and examine correlations among the different events and how these change over time. In this model, we can also examine the impact of baseline Mf burdens prior to treatment and other potential risk factors (age, sex, location, etc.) on AEs.

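### Percent reduction in skin Mf starts from a post-ivermectin count that can be zero; refer it to the Part I count and compare arms at months 12 and 18

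*Combined protocol and SAP*

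**What the plan says.** Secondary efficacy objective 2 (section 4) compares the three regimens on "complete clearance of microfilariae from skin snips 3, 12 and 18 months after treatment with IDA". Section 8.2 gives two skin analyses. One is a logistic-type model for zero Mf at month 18. The other begins "The difference between pre and post treatment MF counts (% reduction" and names a paired t-test, with transformation if needed. It does not say which count is the pre-treatment one and gives no rule for zero counts.

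Three counts could serve:

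- **Part I enrolment.** The entry rule reads "Participants with baseline skin Mf counts ≥ 3 Mf/mg at the time of enrollment into the Part 1 study".
- **The Part I six-month visit.** Section 4.6 makes this the Part II baseline. It follows one ivermectin treatment.
- **A snip before randomisation.** It appears only in the Figure 1 legend (section 4.9), after a second ivermectin treatment. Section 4.7 says that treatment is additional to the "pretreatment with ivermectin given in the Part I study".

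No skin Mf minimum applies to the second or third count. All three arms contain ivermectin (section 4.4). Section 2.2 puts the "nadir of skin Mf between 1 and 3 months post-treatment" and the fall "by 94% after 1 week, and by 98-99% after 1-2 months". It also says that Mf may reappear from month 3.

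**The concern.** Followed as written, the plan takes its pre-treatment count from a time when ivermectin has already lowered skin Mf, as the run-in intends. A person with a zero count has no percent reduction. A person with one or two Mf has a value that a small later change can move by hundreds of percentage points. Without a rule, the analyst must either drop the zeros or choose a denominator after seeing the data. Either choice selects participants by how well the run-in worked.

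The paired t-test adds a second problem. It tests change within persons and does not compare regimens, which is what the objectives ask for.

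Month 3 raises a related issue. It falls at the end of the documented ivermectin nadir in every arm, so clearance there may be high whatever the regimen.

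**Working it through.** **The plan's own figure.** The documents give no expected rate or power for skin Mf. The only sample-size figure concerns nodules: "To achieve 80% power at a two-sided alpha-level of 0.05, we will need nodule histology data from 51 subjects in each treatment group". It "assumed that 30% of the total worms will be fertile females in IVM/ALB group", against 15% with single-dose IDA. The pooled-variance formula without continuity correction gives 121 worms per group. The design effect is 1 + 0.30 × 5 = 2.5, and there are 6 worms per person, so 121 × 2.5 / 6 = 50.4, rounded up to 51. The figure reproduces. It is used below only as an arm size, beside 300 / 3 = 100 per arm.

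**Share with a zero pre-dose count.** Inputs:

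- four snips (section 4.6) of about 2 mg each (section 5.1), so 8 mg of skin;
- suppression of 98-99% (section 2.2), so a residual fraction r of 0.01-0.02;
- r = 0.10 as an assumed case in which Mf have partly returned;
- Part I density D of 3 Mf/mg (the entry minimum) or 10 Mf/mg (illustrative);
- Poisson counts (assumed).

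Formula: P(zero) = exp(−D × r × 8).

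| Part I density | 99% suppressed | 98% suppressed | 10% remaining |
|---|---|---|---|
| 3 Mf/mg | exp(−0.24) = 79% | exp(−0.48) = 62% | exp(−2.4) = 9% |
| 10 Mf/mg | exp(−0.8) = 45% | exp(−1.6) = 20% | exp(−8) ≈ 0% |

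Extra variation between people raises the share at higher densities. With a negative binomial count (assumed k = 0.5) and a mean Part I density of 10 Mf/mg, zeros are 49% at 2% residual and 24% at 10% residual.

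**Instability above zero.** One Mf in 8 mg is 0.125 Mf/mg. If the density later returns to 1 Mf/mg (illustrative), the percent reduction is 100 × (0.125 − 1) / 0.125 = −700%. Against a Part I density of 3 Mf/mg, the same later value gives 100 × (3 − 1) / 3 = 67%.

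**Month-3 clearance.** Let f be the fraction of Mf left just before randomised dosing, and let that dose bring a further 98-99% fall from ivermectin alone. Then P(clear) = exp(−D × f × r × 8). For D from 3 to 20 Mf/mg:

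- f = 0.02: 94-99.5% clear
- f = 0.10: 73-98% clear
- f = 0.30: 38-93% clear

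Power of a two-sided Fisher exact test against an IDA arm with 100% clearance:

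| Comparator clearance (assumed) | 51 per arm | 100 per arm |
|---|---|---|
| 85% | 80% | 99.8% |
| 90% | 40% | 94% |
| 95% | 4% | 38% |

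**The case against.** The strongest reply has four parts.

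1. **The pre-treatment count is undefined, so the problem depends on a reading.** If section 8.2 meant the Part I enrolment count, nobody starts at zero. This is true, but section 4.6 names the Part I six-month visit as baseline, and a reader following the text would use it. A raw difference in counts is also defined at zero, but section 8.2 labels the quantity a percent reduction.
2. **The high zero shares need nadir suppression.** Section 4.1 places randomised dosing 5.5 to 12 months after ivermectin, when Mf may have returned. Section 4.9 gives about 20 months on study with 18 after treatment, which suggests roughly 2 months. These passages need reconciling. Until then the whole range in the table is open, and this part of the reply stands.
3. **The plan already leans towards the later visits.** Section 8.2 models zero Mf at month 18 only, and its skin population is defined at months 12 and 18. This also stands. Month-3 clearance is an objective without a stated comparative analysis.
4. **A Part I reference folds the run-in ivermectin into the reduction.** This is correct, and it is why the paired test cannot be kept with that reference.

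A reader might infer that skin Mf are near zero before dosing and that month 3 cannot separate the regimens. The documents do not support this. They describe counts as low or greatly reduced, give no Part II skin figures and mention reappearance from month 3. At 85% comparator clearance, a perfect IDA arm would be detected with 80% power at 51 per arm. A reader might also infer that objective 3 is restricted to people clear at month 3, but the objective states no such condition.

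**Conclusion.** The percent-reduction analysis needs correction. On the baseline the plan names, or on the later pre-randomisation snip, the denominator is a post-ivermectin count with no minimum. The measure is therefore undefined for some participants and unstable for others. How many depends on the residual density, which the documents do not give. With 8 mg of skin and Poisson counts, the share with a zero ranges from about 0% or 9% (10 or 3 Mf/mg, 10% remaining) to 45% or 79% (99% suppression). The paired t-test does not answer a between-regimen question under any choice of denominator.

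On month 3 the conclusion is more limited. Clearance is likely to be near ceiling with little power, but how near depends on an unstated comparator rate. The shared run-in reduces the contrast between arms and does not bias the randomised comparison. The primary nodule endpoint is unaffected.

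**What to change.** In section 8.2:

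- Define the reference for percent reduction as the Part I pre-ivermectin density, which inclusion criterion 3 keeps at 3 Mf/mg or more.
- Replace the paired t-test with a between-arm comparison of Mf density, or of percent reduction from that reference, at months 12 and 18. Adjust for Part I density and keep every participant with snips. A count model with skin weight as an offset would retain zeros without a special rule.
- Report month-3 clearance descriptively, and state that a null result there is not evidence of no IDA benefit.

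The cost is a change of SAP wording, reported as section 8.3 requires for major changes. It uses data already held from Part I and needs no extra visit or sample. The downside is that the within-arm reduction then includes the ivermectin given before randomisation, so only the between-arm contrast can be interpreted. The SAP should say so.

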4.1 Study Design

This is an open label, randomized clinical trial will be conducted in Ghana. The goal will be to enroll up to 300 eligible participants with microfiladermia. Some participants who have met the inclusion criteria (see Study Enrollment, below) will have intraocular Mf visible by slit lamp at baseline prior to IVM pre-treatment. Participants will be recruited from an on-going related study that is evaluating the kinetics of Mf clearance from the eye and skin after treatment with IVM. Participants will be treated with ivermectin at baseline in this study and then randomized into three treatment arms 6 months (with a window of 5.5 months to 12 months) after treatment with IVM:

1. IVM with albendazole (the comparator)
2. A single dose of IDA
3. Three daily doses of IDA

Each arm will be stratified with respect to the presence ocular Mf six months after their first IVM pre-treatment (i.e. in “Part I”, a preceding study) or at the baseline assessment in the Part II study. Participants will be closely monitored to determine whether the treatments are safe. Efficacy will be assessed by performing skin snips for detection of Mf and by histological examination of adult worms in onchocercal nodules surgically removed 18 months after treatment with IDA.

All participants will be treated again with ivermectin at the time of consenting for the Part II study to further ensure that they have low skin and ocular Mf counts at the time of enrollment and randomization to treatment arms. Treatment with ivermectin is widely accepted as a standard of care for MDA programs, and should not present undue risk.

Study Enrollment

Participants will be recruited from an on-going related study of the kinetics of Mf clearance from skin and eyes after ivermectin treatment (Part I). Participants from that study with baseline skin Mf counts ≥ 3 Mf/mg will be invited to participate in this “Part II” study.

Study Population - Participants will be recruited from the Nkwanta North and South Districts in the Volta region of Ghana. Most participants will be recruited from Kpassa town or villages in Kpassa sub-district along the Kpassa river basin that are endemic for onchocerciasis. Residents are mainly of the Konkomba ethnic group. The local language is Konkomba, however most residents also speak and understand the Twi language. Bi-annual MDA with IVM in the area started in October 2017. The target number of participants for the study will be up to 300.

